4.2 Exclusion Criteria

Patients not meeting the inclusion criteria above will not be included in the study. No other exclusion criteria will be used.

4.3 Recruitment and retention

4.3.1 *Informed consent considerations*

We have received a waiver of informed consent and HIPAA authorization for all physician-subjects and patient-subjects in this study. The goal of this project is to improve existing decision support to reduce the use of potentially dangerous medications in the elderly, consistent with numerous professional guidelines and quality metrics. Providers will retain oversight of their patients' care and will be able to make therapeutic choices based using their professional judgement. Patients will not receive any direct intervention as a result of their inclusion in the study.

4.3.2 *Inclusivity of study subjects*

Physician and patient subjects will be included based on their meeting eligibility criteria as part of routine care, and the study population will be highly inclusive. We expect these participants to cover a broad range of participants by gender and race/ethnicity. Given the minimal risk nature of the study, participants will not receive incentives, remuneration, or be required to provide informed consent.

5. Study Interventions

5.1 Therapeutic areas

The focus areas for the EHR tools will be primarily drawn from the outpatient Choosing Wisely recommendations in geriatric medicine but are also informed by the Beers Criteria and other major clinical guidelines.^{4,23} In specific, we plan to focus on the following therapeutic

classes: (1) benzodiazepines; (2) sedative hypnotics (sleep medicines) and (3) anticholinergics.

5.2 Study interventions

Physicians in the replication trial randomized to one of the 2 active intervention arms will receive one of several possible enhanced EHR decision support to guide care. The type and timing of an alert will vary based on the intervention are outlined below. The two specific EHR tools for the replication trial at MGB was determined based on the adaptive randomized trial results:

Arm	Alert type	Open encounter	Follow-up booster	Pre-commitment
1	Enhanced	X	X	
2	Enhanced	X		X
Usual care	None			

Arms 1 through 2 are enhanced EHR tools to encourage the deprescribing of the medications under study. Physicians randomized to usual care will receive no intervention.

The central component of Arms 1 through 2 will be an enhanced EHR alert (known as a Best Practice Advisory [BPA]). The enhanced BPA will appear on each provider's EHR screen and will contain several standard components. The BPA will:

1. give providers information about why the medication is dangerous for their patient using the behavioral science principle of salience to make this information as impactful as possible;
2. include a set of tips to help providers discuss medication discontinuation with their patients;
3. ask providers to select an acknowledgment reason if they decided not to discontinue the medication;

4. include a SmartSet order set that will allow providers to order a gradual dose taper for their patient, which limits risks of withdrawal symptoms for the patients for benzodiazepines and sedative hypnotics, order alternative medications, place a referral to a behavioral health specialist, provide instructions on how to make lifestyle modifications to improve patient symptoms, and add customizable patient instructions for how to gradually taper off benzodiazepines and sedative hypnotics, as applicable.

We will also test several other modifications to this enhanced BPA. In specific, as outlined in the table above, we will add in a boosting option in the enhanced BPA in Arm 1, which is a provider-directed option for a follow-up in-basket message sent 4 weeks after the BPA is triggered. Arm 2 will test the use of a two-staged pre-commitment BPA in which the providers are prompted to discuss risks of these high-risk medications and share a handout about the risks with their patients, at their own discretion.

If patients are eligible for alerts to be fired for multiple therapeutic classes of interest (e.g., benzodiazepines and sedative hypnotics), the EHR tools will appear for both classes separately.

5.3 Measures to minimize bias: randomization and blinding

Providers will be randomized to treatment arms in equal proportions based on blocks. We will use provider-based cluster randomization to minimize the possibility of contamination in study interventions between practices and clinic staff. For the randomization, we will use stratified randomization based on clinic practice size and baseline rates of prescribing to reduce potential imbalances between the providers assigned to the treatment arms.

The providers will not be blinded to which arm they were assigned to, as blinding is the context of an intervention that is intended to motivate action will be infeasible. The study

analyst will generate and implement the randomization scheme, with oversight by the Principal Investigators. Investigators will be blinded to the treatment arms during interim and final analyses.

6. Study Assessments and Procedures

6.1 Baseline data

We will collect baseline data on patients and providers using extracted EHR data and/or administrative claims data as applicable for the study aim. This baseline data will be used to assess any potential imbalances in the characteristics of providers or patients despite randomization. The baseline data will include, but are not limited to: gender, baseline rates of prescribing, practice location, and patient case-mix. We will also collect patient data that include but are not limited to: sociodemographic data, medical history and comorbidities, baseline resource utilization in prior 12 months (i.e., number of visits), biometric values (e.g., serum creatinine, systolic/diastolic blood pressures).

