3.2 Overall design

We will conduct a parallel group trial at Mass General Brigham, specifically within MGH primary care practices. We hypothesize that these tools will reduce prescribing of high-risk medications (primary outcome), cumulative prescribing of high-risk medications (secondary outcome), and clinically-significant adverse drug events like sedation and confusion (tertiary outcome) compared with usual care.

3.2.1 *Trial Design*

[figure not shown]
This trial is a cluster-randomized, NIH-defined Phase III pragmatic trial. The study statistician, in partnership with data analysts at MGB, will generate and implement the randomization scheme, with oversight by the Principal Investigators. All the study sites will be at MGH for this trial; we have received approval from leadership at MGH primary care practices and Digital Health eCare teams to conduct this trial. For study evaluation, data regarding patients' medical history, disease control, medication use, and healthcare utilization will be obtained from EHR data or administrative claims data. Any administrative claims data used for evaluation in this study will come directly from MGB in HIPAA-limited datasets through their risk-bearing contracts.

We will randomize primary care providers at MGH to one of the 2 most promising treatment arms identified in the prior adaptive randomized trial conducted at Atrius Health or usual care (described in further detail in 5.2). We expect to randomize approximately 200 providers. Providers randomized to one of the 2 selected treatment arms will receive an EHR tool to guide their care of eligible patients. We will randomize providers based on provider demographic characteristics, patient case-mix factors, and baseline rates of high-risk medication prescribing measured in EHR data.

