6.2 Outcomes

The primary outcome will be a binary composite measure of a reduction in inappropriate prescribing, evaluated using EHR data. In specific, we will measure a composite of 1) discontinuation of high-risk medications (benzodiazepines, sedative hypnotics, or anticholinergics) defined by either: a) active discontinuation and no subsequent order or b) no order during follow-up or 2) ordering a gradual dose taper (for benzodiazepine or sedative hypnotics). Our primary analyses will be within patients who had a visit (telemedicine or in-person) with a study provider after randomization. If either of these actions is taken by providers for a specific patient at any point in the follow-up window, we will classify the patient as having had a reduction in inappropriate prescribing. If the patient has multiple therapeutic classes of interest (e.g., benzodiazepines and sedative hypnotics), we will classify patients with a reduction for any class as a “reduction” for the composite measure. We will also stratify

patients by their number of eligible therapeutic classes (i.e., one, two, or three classes) and analyze outcomes within these strata.

Secondary outcomes include the quantity of high-risk medication prescribed, defined by number of pills of high-risk medications (all three classes) prescribed to patients in the follow-up period and number of lorazepam milligram equivalents of benzodiazepines and sedative hypnotics to capture cumulative prescribing by all providers. As above, we will also stratify patients by their number of eligible therapeutic classes (i.e., one, two, or three classes) and analyze outcomes within these strata.

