7.2 Sample size determination

We should have >80% power to detect absolute differences of 10% or smaller in the reduction in prescribing between each intervention arms and usual care, assuming an intra-provider correlation of 0.1 (which is based on prior work including the Atrius trial) and a baseline rate of the primary outcome of 25% in the usual care arm. We plan to use Holm-Bonferroni correction to account for multiple testing between each of the intervention arms and usual care, but we will be powered even if using a Bonferroni correction. Our assumptions will also be robust to a slightly higher baseline rate of the primary outcome in the usual care arm. We should also be sufficiently powered to detect meaningful differences in the clinically significant adverse events.

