7.3 Statistical analyses

7.3.1 *Analysis of the primary endpoints*

The unit of analysis is at the patient-level. All analyses will use intention-to-treat principles. We will use generalized estimating equations to adjust for clustering and repeated observations per provider to evaluate the effectiveness of the intervention arms versus usual care. For the inappropriate prescribing outcome, we will use a log link function and binary distributed errors. These models generate the estimated relative risks (RRs) with robust standard errors and are considered to be particularly appropriate when outcomes are common (e.g., incidences of $\geq 10\%$). Because this is a randomized trial, our primary analyses are

planned as unadjusted; however, in secondary analyses, we will adjust for patient age, race/ethnicity, and gender.

Given the nature of the data and how the outcomes are categorized, there will not be missing values for the primary endpoint, as the absence of action is classified as no action by the provider. For the primary analysis, we will include all eligible patients in the denominator who had at least one visit with their primary care provider. In secondary analyses, we will include all eligible patients of those primary care providers in the denominator, regardless of whether the patient visited the provider over the follow-up period.

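### The plan makes no use of each provider's own past stop/taper rate; adding it to the unadjusted primary model would be a cheap gain in precision, of uncertain size

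*Combined protocol and SAP*

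**What the plan says.** **Baseline.** Section 6.1 lists the provider data: "The baseline data will include, but are not limited to: gender, baseline rates of prescribing, practice location, and patient case-mix". The list is open, but a past stop/taper rate is not on it. Section 5.3 says "we will use stratified randomization based on clinic practice size and baseline rates of prescribing to reduce potential imbalances". Section 3.2.1 gives a different set of randomisation factors, ending in "baseline rates of high-risk medication prescribing measured in EHR data". The schedule in 3.8 marks prescribing under follow-up only.

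**Outcome.** Section 6.2: "The primary outcome will be a binary composite measure of a reduction in inappropriate prescribing, evaluated using EHR data". It is scored per patient, as a discontinuation or a taper order, among patients who under 4.1 already have substantial recent prescribing of these drugs.

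**Model.** Section 7.3.1: "We will use generalized estimating equations to adjust for clustering and repeated observations per provider", with a log link. The primary analyses are "planned as unadjusted; however, in secondary analyses, we will adjust for patient age, race/ethnicity, and gender". Section 7.3.5 adds provider, patient and practice characteristics in further secondary analyses. Its examples do not include a past value of the outcome.

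**Power.** Section 7.2 claims more than 80% power for differences of 10 points or smaller, from 25% under usual care, "assuming an intra-provider correlation of 0.1 (which is based on prior work including the Atrius trial"). It takes no credit for a baseline covariate.

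**The concern.** How many older adults a provider treats with these drugs and how often that provider stops them among existing users are different quantities. A provider may prescribe to many and also stop many. Balancing on the first therefore need not balance the second.

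The plan expects providers to differ in stopping, since it assumes an intra-provider correlation of 0.1. To the extent that those differences persist from one year to the next, a provider's past stop/taper rate predicts the follow-up rate. It could be derived from the EHR data that the trial already extracts. Because the primary model has no covariates, any variance that this rate could explain stays in the standard error. At stake are the width of the primary interval and some power, in a trial whose stated power depends on a cluster size that is not given.

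**Working it through.** **Inputs from the plan.** About 200 providers in three equal arms (3.2.1, 5.3), so 66 per arm is used; 25% against 35% and ICC 0.1 (7.2); two comparisons with usual care under Holm-Bonferroni (7.2).

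**Assumptions.** Overall two-sided alpha 0.05, hence 0.025 per comparison (the level is not stated); m analysed patients per provider; r, the correlation between a provider's true stop/taper rates in the year before and the year after randomisation. Section 4.1 admits providers with a single qualifying older patient, so small m is included.

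**Step 1: the plan's own power figure.** With independent patients, 80% power needs 398 per arm at alpha 0.025. With clustering, effective n = 66m / [1 + (m − 1) × 0.1].
- m = 13: 858 / 2.2 = 390, just short.
- m = 14: 924 / 2.3 = 402, enough.
- With unequal panels (coefficient of variation, CV, 0.6), the design effect is 1 + [(1 + 0.36)m − 1] × 0.1. At m = 30 it is 4.98, and 1980 / 4.98 = 398.

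The claim of more than 80% can thus be met at about 14 patients per provider with equal panels, or about 30 at CV 0.6. Without m it can be neither reproduced nor refuted.

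**Step 2: effect of the covariate.** An observed provider rate from m patients has reliability R = 0.1m / [1 + 0.1(m − 1)]. If the baseline panel is also of size m, adjustment multiplies the variance of a provider mean by 1 − (rR)². For m = 15, R = 1.5 / 2.4 = 0.625. At r = 0.5, (0.5 × 0.625)² = 0.098, so effective n rises from 990 / 2.4 = 412.5 to 412.5 / 0.902 = 457.

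Power for 25% against 35%, equal panels, with the variance reduction in brackets:

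| m | R | unadjusted | r = 0.3 | r = 0.5 | r = 0.7 |
|---|---|---|---|---|---|
| 5 | 0.36 | 55.1% | 55.7% (1%) | 56.6% (3%) | 58.2% (6%) |
| 10 | 0.53 | 73.8% | 75.0% (2.5%) | 77.2% (7%) | 80.4% (14%) |
| 15 | 0.62 | 81.5% | 83.0% (3.5%) | 85.6% (10%) | 89.5% (19%) |
| 20 | 0.69 | 85.5% | 87.1% (4%) | 89.9% (12%) | 93.7% (23%) |

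At m = 20 the detectable difference goes from 9.3 points to 8.7 (r = 0.5) or 8.1 (r = 0.7).

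**Step 3: simulation.** The formula is a linear approximation, so the design was also simulated with log-link Poisson regression and provider-clustered robust standard errors, with and without the observed pre-period rate.
- Variance reduction for r = 0.5 to 0.8: 2-7% at m = 5, 6-19% at m = 10, 9-20% at m = 15, and 9-27% at m = 15 with CV 0.6. At r = 0.3 it is about 2%.
- Separate simulations do not agree exactly. At m = 10 and r = 0.8 they gave 12% and 19%; the formula gives (0.8 × 0.526)² = 18%.
- Power, 1,000 runs per case, for m = 15 with equal panels: 82% to 86% (r = 0.5) and 82% to 92% (r = 0.8). With CV 0.6: 74% to 78% and 72% to 86%.
- At r = 0, power was 82% in both models.
- Under the null (m = 15, CV 0.6, r = 0.8; 2,000 runs), rejection was 2.6% unadjusted and 2.9% adjusted. The Monte Carlo error is √(0.025 × 0.975 / 2000) = 0.35 points, so both are compatible with 2.5%.
- The mean RR was 1.40 to 1.41 in both models at m = 15.

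**The case against.** The strongest reply is that nothing here is wrong. The unadjusted GEE is prespecified, randomisation and provider-clustered robust errors make it valid, and 7.2 already carries the full ICC. That stands.

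Further points that stand in whole or in part:
- **Stability is not established.** A reader might infer from the ICC of 0.1 that providers differ stably in stopping. It describes correlation within one period and says nothing about agreement between years. At r = 0.3 the gain is under 2 power points at every m checked.
- **Cohort formation may lower r.** Section 4.1 enrols patients with recent prescribing, so patients stopped earlier tend to be absent from the trial cohort. A provider who stopped many may be left with patients who are harder to stop. The simulations omit this.
- **Baseline and follow-up measures differ somewhat.** The order set in 5.2 eases taper ordering in the intervention arms and was not part of the pre-period.
- **Imbalance is not unchecked.** A reader might infer that it is. But 6.1 says baseline data will be used to assess imbalance, and its list is open, as are the examples in 7.3.5. The accurate statement is that the past outcome is not named or planned for use.
- **The wording is not fully settled.** Section 7.1 glosses provider prescribing rates by evidence of a reduction. Section 3.2.1, however, makes clear that the balancing variable is the rate of high-risk prescribing.
- **Convergence.** With this continuous covariate, 6 of 200 log-binomial fits failed at m = 10, r = 0.8, so a fallback is needed.

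What does not stand is that the covariate carries a statistical penalty: no power was lost at r = 0, and the RR and type I error did not change materially.

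**Conclusion.** The point holds as a missed, low-cost gain in precision, not as an error. The plan names a prescribing rate as provider baseline, leaves the provider's past value of the primary outcome unnamed, and fits the primary model without covariates. The loss arises from the unadjusted model in 7.3.1: collecting the rate under 6.1, without modelling it, would not narrow the primary interval.

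The size runs from almost nothing (r near 0.3, or m near 5) to a variance reduction of roughly a fifth at m = 15 and r = 0.8, and up to 27% there with unequal panels. All of this rests on assumed m, r and alpha. The documents do not support reading it as bias, an invalid test, a wrong choice of stratifier or a failed power claim.

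**What to change.** Before outcome data are seen:

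1. **7.3.1.** Add one prespecified provider-level covariate to the primary log-link GEE: the 6.2 outcome rate from EHR data for the 12 months before randomisation, in patients who met the 4.1 patient criteria at the start of that year and had a visit. Because the log-link RR is collapsible, the target remains the same ratio.
2. **Fallback.** If the log-binomial fit does not converge, use a Poisson log-link model with provider-clustered robust standard errors.
3. **Providers without history.** Assign the overall mean and add an indicator.
4. **Sensitivity.** Keep the unadjusted model.
5. **6.1.** List the rate among the baseline data. Using it as a stratifier in 5.3 is optional, and possible only if allocation has not been generated.

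**Cost.** SAP wording and one further run of the outcome code, on about 18 months of history (12 months plus the 180-day look-back). The primary model is no longer unadjusted. Historical provider-patient assignment must be retrievable, which the documents do not confirm and should be checked first. The return may be small if panels are small or stopping rates unstable.

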6.2 Outcomes

The primary outcome will be a binary composite measure of a reduction in inappropriate prescribing, evaluated using EHR data. In specific, we will measure a composite of 1) discontinuation of high-risk medications (benzodiazepines, sedative hypnotics, or anticholinergics) defined by either: a) active discontinuation and no subsequent order or b) no order during follow-up or 2) ordering a gradual dose taper (for benzodiazepine or sedative hypnotics). Our primary analyses will be within patients who had a visit (telemedicine or in-person) with a study provider after randomization. If either of these actions is taken by providers for a specific patient at any point in the follow-up window, we will classify the patient as having had a reduction in inappropriate prescribing. If the patient has multiple therapeutic classes of interest (e.g., benzodiazepines and sedative hypnotics), we will classify patients with a reduction for any class as a “reduction” for the composite measure. We will also stratify

patients by their number of eligible therapeutic classes (i.e., one, two, or three classes) and analyze outcomes within these strata.

Secondary outcomes include the quantity of high-risk medication prescribed, defined by number of pills of high-risk medications (all three classes) prescribed to patients in the follow-up period and number of lorazepam milligram equivalents of benzodiazepines and sedative hypnotics to capture cumulative prescribing by all providers. As above, we will also stratify patients by their number of eligible therapeutic classes (i.e., one, two, or three classes) and analyze outcomes within these strata.

Tertiary outcomes will include the extent to which medications are filled and consumed by patients, as measured within the subgroup of patients with claims data. In specific, these outcomes will be conducted among the large subgroup of patients funded by Medicare, including pharmacy claims via the secure MedRIC data enclave. In particular, we will measure the quantity of high-risk medication dispensed, defined by number of milligram equivalents of high-risk medications filled by patients, in follow-up, using pharmacy claims data. Other tertiary outcomes will include the occurrence of clinically-significant adverse drug events, including but not limited to, sedation or cognitive impairment, and all-cause hospitalizations and falls or fractures, measured in administrative claims data. These clinical outcomes will be evaluated using validated and CMS-driven ICD-10-CM diagnosis and procedure-based algorithms applied to these patients' medical and pharmacy administrative claims data. Because the sensitivity of clinical outcomes in EHR systems is known to be low (e.g., because patients may seek subsequent care at other healthcare systems), using routinely-collected data from insurers overcomes this limitation.²⁴ We will also evaluate implementation of the intervention using structured deidentified data from the EHR about use of the EHR system, which will help inform how to scale the interventions (see Data to be collected form).

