To determine whether EHR-tools designed using behavioral science principles are more effective than at reducing inappropriate prescribing of high-risk medications in older adults than standard EHR tools or usual care.	Composite of 1) discontinuation of high-risk medications (benzodiazepines, sedative hypnotics, or anticholinergics) or 2) ordering a gradual dose taper for one of these medications	These outcomes are rapidly measurable using EHR data alone and will provide evidence of provider behavior change.
Secondary		
To examine whether behavioral science-based EHR tools reduce cumulative prescribing of high-risk medications in older adults compared with usual care.	Quantity of high-risk medication prescribed, defined by number of pills and milligram equivalents of high-risk medications prescribed to patients in follow-up	These outcomes capture the extent to which high-risk medications are cumulatively prescribed to patients by all providers over the follow-up period.
Tertiary/Exploratory		
To evaluate whether behavioral science-based EHR tools reduce the risk of clinically-significant adverse drug events, falls, fractures, hospitalizations, or emergency room visits compared with usual care.	Rates of adverse drug events, falls, fractures, hospitalizations, and emergency room visits in follow-up; quantity of high-risk medications dispensed to patients in follow-up period	These outcomes measure clinical outcomes that are consequences of these high-risk medications, measured in medical and pharmacy administrative claims data.

3. Study Design

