3.5 Justification for intervention

The focus areas for the EHR tools will be primarily drawn from the outpatient Choosing Wisely recommendations in geriatric medicine but are also informed by the Beers Criteria and

other major clinical guidelines.¹⁶⁻¹⁸ In specific, we plan to focus on the following therapeutic classes: (1) benzodiazepines; (2) sedative hypnotics (sleep medicines) and (3) anticholinergics. These classes were chosen because they all have established clinical guidelines recommending reductions in use, continue to be heavily over-prescribed, contribute significantly to poor clinical outcomes in older adults, and also have non-drug or less risky therapeutic alternatives. While prescribing non-drug options may be the optimal alternative to these potentially inappropriate medications, their adverse effects could also be attenuated by choosing alternative medications in a different drug class, lower doses of medication, or alternative, safer medications within the same drug class.

We have chosen to focus on key principles of behavioral economics and cognitive psychology to “nudge” providers to optimize prescribing, such as timing, salience, framing, simplification, pre-commitment, and boosting. These principles were selected based on their effectiveness in other settings¹⁹⁻²², their applicability to the care of older adults, and their ability to be adapted to the EHR context.

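### One of the two secondary quantity measures is a raw pill count: it misses changes in tablet strength, can rise during a taper, and is all that section 6.2 gives for anticholinergics

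*Combined protocol and SAP*

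**What the plan says.** Section 6.2 defines the secondary outcome by two measures. The first is a count "defined by number of pills of high-risk medications (all three classes) prescribed to patients in the follow-up period", with no adjustment for strength. The second is the "number of lorazepam milligram equivalents of benzodiazepines and sedative hypnotics". Anticholinergics are not in the second measure. Results are to be stratified by how many classes a patient is eligible for, not by which class.

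Two other places describe milligram equivalents more broadly:
- The objectives table in section 2 has the same secondary endpoint "defined by number of pills and milligram equivalents of high-risk medications prescribed to patients in follow-up".
- The tertiary dispensing outcome in section 6.2 is "defined by number of milligram equivalents of high-risk medications filled by patients, in follow-up, using pharmacy claims data", for patients with Medicare claims.

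Neither limits the measure by class, and neither gives a conversion for anticholinergics.

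On the prescribing actions that bear on this, section 3.5 lists among the ways to lessen harm "lower doses of medication, or alternative, safer medications within the same drug class". Section 5.2 says that the alert in both tool arms will "include a SmartSet order set that will allow providers to order a gradual dose taper for their patient"; usual care receives no tool. In the primary composite, a taper order counts for benzodiazepines and sedative hypnotics only, and it counts whenever in follow-up it is placed.

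**The concern.** A pill count measures drug exposure only if strength per tablet stays the same. Lowering the dose, which section 3.5 names, and tapering, which the tool prompts, can both be written in weaker tablets. The count then stays level or rises while the patient receives less drug.

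Three things are at stake:

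- **Direction by arm.** The taper order set exists only in the tool arms. Usual-care clinicians may still taper unprompted, but the tool is meant to make it more common. A distortion from smaller tablets would therefore tend to make the tools look worse.
- **Two measures, one objective.** Pills and milligram equivalents can move in opposite directions, and neither is named as leading. The Holm-Bonferroni procedure in section 7.2 covers the two arm comparisons, not a choice between quantity measures. A conflict would be settled after the data are seen.
- **Anticholinergics.** Section 6.2 gives this class no dose-based measure against which to read the pill count.

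**Working it through.** The plan states no effect size or power for the quantity outcomes, so there is no figure of its own to reproduce. Section 7.3.2 analyses quantity with an identity link and normal errors, so the contrast is a difference in means. A patient whose count rises offsets one whose count falls.

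**Inputs.** Follow-up is 12 months (sections 3.2.1 and 3.6), taken as 365 days. The rest is assumed for illustration and is not a regimen: one tablet a day of strength 1 at baseline, and new tablets of strength 1/k.

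**Formulas.** For phases of d days at fraction f of the baseline amount:
- drug amount = sum of d × f
- pills = sum of d × f × k, where k = 1 for days on the original tablet

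Continuing unchanged gives 365 pills and 365 units of drug.

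**Strength change at the same frequency** (k = 2, f = 0.5 all year): pills 365 × 0.5 × 2 = 365; drug 365 × 0.5 = 182.5.

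**Twelve-week taper in quarter-strength tablets** (k = 4; 28 days each at 75%, 50% and 25%, then none): pills 28 × (3 + 2 + 1) = 168; drug 28 × (0.75 + 0.50 + 0.25) = 42.
- Begun at randomization: 168 pills and 42 units over the year.
- Begun with 12 weeks left: 365 - 84 = 281 days unchanged, so pills 281 + 168 = 449 and drug 281 + 42 = 323.

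**Year-long step-down in half-strength tablets** (k = 2; 91, 91, 91 and 92 days at 100%, 75%, 50% and 25%): pills 182 + 136.5 + 91 + 46 = 455.5; drug 227.75.

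| Illustration | Pills vs 365 | Change in pills | Change in drug |
|---|---|---|---|
| Half strength, same frequency | 365 | 0% | -50% |
| 12-week taper, begun at randomization | 168 | -54% | -88% |
| 12-week taper, begun with 12 weeks left | 449 | +23% | -12% |
| Year-long step-down | 455.5 | +25% | -38% |

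**When does the count rise?** If the new tablets are used all year, pills relative to baseline equal k times the mean fraction over the year, so a rise needs that product to exceed 1. For the 12-week taper begun on day s, it needs s + 168 > 365, that is, a start after about day 197. With k = 1 (fewer tablets of the original strength), pills and drug fall by the same proportion and there is no distortion.

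**Link to the primary outcome.** A taper ordered late in follow-up makes the patient a primary success. In the third row, the same patient shows a rise on the pill measure.

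**Scope of milligram equivalents.** The section 6.2 secondary outcome restricts them to two classes. The objectives table and the tertiary dispensing outcome apply them to high-risk medications without restriction. Lorazepam equivalents have no stated meaning for anticholinergics, and no other reference is given.

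**The case against.** The strongest reply is that the plan already handles the main case. Tapers concern benzodiazepines and sedative hypnotics, and those are the classes with a milligram measure. This stands. A reader might infer that the secondary outcome as a whole is a raw pill count; it is not. What remains for these two classes is the missing lead measure.

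Second, a reader might take the 12-week taper to double the pill count, since 168 compares with 84 over those 12 weeks. The outcome runs for 12 months, however. Begun at randomization, that taper shows a fall, though an understated one. A reversal needs a late start or a slow step-down.

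Third, no passage says that the order set or the providers use weaker tablets. Fewer tablets of the same strength do show in the count. The documents therefore do not support the inference that no anticholinergic dose reduction can be seen; only a change of strength is hidden. Nor does section 5.2 list an anticholinergic dose reduction among the tool's actions, so a bias by arm is not shown for that class. The gap there rests on the general remark in section 3.5.

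Fourth, a reader might infer that the document offers nothing but pills for anticholinergics. The objectives table and the dispensing outcome name milligram equivalents without a class limit, which nominally includes them. But neither defines a conversion, and the second covers dispensing in the claims subgroup only.

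Last, pills and milligrams can be complementary. That supports keeping both; it does not settle in advance which is read first.

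**Conclusion.** The point holds in this limited form. One of two secondary quantity measures ignores strength: it misses a strength change completely (0% against -50%) and understates a taper in smaller tablets (-54% against -88%) or reverses it (+23% against -12%). These are one-patient illustrations under assumed tablet strengths and schedules. The effect on the arm means depends on how many patients change strength, which the documents do not give. The likely direction is against the tools, because only they prompt tapers, but an actual bias is not demonstrated. For benzodiazepines and sedative hypnotics the remedy is already in the plan and only needs to be given precedence. For anticholinergics, the section 6.2 secondary outcome is pills alone, while two other places imply a dose-based measure that is never defined. The primary outcome is unaffected. This is a worthwhile, cheap improvement to a secondary outcome, not a threat to the trial's main conclusion.

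**What to change.** 1. Reconcile the objectives table in section 2 with the secondary and tertiary definitions in section 6.2 on whether milligram equivalents include anticholinergics.
2. Name lorazepam milligram equivalents as the lead quantity outcome for benzodiazepines and sedative hypnotics.
3. For anticholinergics, prespecify a strength-standardised quantity: milligrams ordered divided by a fixed reference amount for each drug, summed within the class. The reference is a unit of measurement only. A fixed reference stays defined after a switch to another drug, whereas the patient's own baseline tablet strength does not.
4. Report quantities by class, with anticholinergics separate, and keep raw pills as a supportive measure.

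The cost is revised outcome wording, a reference table for the anticholinergics and a unit that is less simple than pills. The strength data are those that the milligram-equivalent measure already requires. The changes should be fixed before outcome data are examined.
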